## REVISION HISTORY

Version Date	Revision summary	Protocol		Consent		Other	
		Revised	Version Date	Revised	Version Date	Revised?	Version Date
5/25/2009	original to IRB		5/9/2009		11/15/07		11/15/07
10/20/09	Revisions from start-up meeting - eliminate visit 2 ■	Amend ment 1	10-20- 09		10/29/09		
11/25/2009	Final Protocol		12/31/20 09				
4/5/2010	Amendment 1 Increase payment to \$100; change advertisement Revised product list to change Skoal bandits straight to Skoal bandits wintergreen		4/5/2010		3/25/2010		
7/13/11	Updated tobacco product list for eligibility and on page 9		7/13/11	NA			NA

## **A. Specific Aims**

Reducing toxicants in tobacco products and establishing performance standards for tobacco products have been discussed and recommended by the World Health Organization Tobacco Regulation Study Group and by tobacco control scientists and advocates [1, 2]. Although the focus to date has been primarily on cigarettes, reducing tobacco toxicants in smokeless tobacco should also be strongly considered and recommended [3]. The extent of toxicity varies considerably across different brands of smokeless tobacco (ST) products and data suggest that greater toxicity may result in greater health risks. However, little is known about the actual extent of human exposure to toxicants from current ST products and factors that might moderate the extent of this exposure. The overall goals of this study are to determine toxicant exposure across brands of ST that vary in levels of nicotine and TSNAs using a panel of biomarkers of exposure and effect, and to examine factors other than product toxicants that influence the extent of this exposure.

## **B. Research Design and Methods**

### **B1. Overview**

Subjects using the brands listed in Table 2 will be recruited from three different regions in the U.S. They will undergo two assessment sessions. During these sessions, urine and blood samples will be collected. During the time of data collection, ST users will be recording the amount of tobacco products that they use on a daily basis using their diary cards.

### **B2. Procedures**

*Subject recruitment.* Subjects (N=600) will be recruited from a) Minneapolis/St. Paul, MN, b) Eugene, OR, and c) Morgantown, WV. Each site will recruit 200 subjects over the course of 2 years, with a total of 100 subjects recruited for each brand that is listed in Table 2. We anticipate no problems with recruitment. Surveys conducted in 2007 or 2006 estimated Minnesota and Oregon male ST prevalence of 6.0% and 6.5%, respectively. The 2006 West Virginia Adult Tobacco Survey estimated the male ST prevalence to be about 16%. Multiple avenues of recruitment will be pursued to ensure as representative of a sample as possible. These methods include radio, cable, newspapers (want ads and display ads), restroom stall ads, sporting good stores, WIC clinics, internet and press releases. The recruitment advertisements will state that daily ST users are needed for a study that examines the effects from ST use; blood (only at U of MN site), oral cells (only at U of MN site) and urine samples will be obtained. It will further state that subjects will be paid for participation. Potential adult subjects will be asked to call the research clinic number where the study will be explained, brief phone screening will be conducted, and interested and potentially eligible subjects will be asked to attend an orientation meeting. The brands of ST will not be listed on the advertisements to ensure that we are recruiting actual users of the brands rather than subjects who falsely claim using one of the brands of interest in order to obtain money for study participation. Subjects will be informed that the study determines the extent of exposure to toxicants and the effects of these exposures across different brands of ST.

#### ***B2a. Subject inclusion/exclusion criteria***

Adult ST users (18 years or older) who are interested in the study will telephone the research clinics, be informed about the study, and initially screened in order to determine whether they meet specific inclusion/exclusion criteria.

Inclusion criteria include:

- a) use of a consistent brand and daily amount of ST for the past 6 months;
- b) in good physical health (no unstable medical condition and no kidney or liver disease);
- c) stable, good mental health (e.g., no recent unstable or untreated psychiatric diagnosis, including substance abuse, as determined by the DSM-IV criteria).
- d) use of one of the following smokeless tobacco products:

(UPDATED BRANDS BY GROUP): 1) Camel Snus, Marlboro Snus; 2) Skoal Long Cut Mint, Skoal Fine Cut Original, Copenhagen Long Cut Original, Kodiak Wintergreen, Skoal Bandits Wintergreen, Skoal Pouches Straight, Skoal Pouches Wintergreen; 3) Grizzly Long Cut Straight, Skoal Long Cut Straight, Grizzly Long Cut Mint, Grizzly Long Cut Wintergreen, Grizzly Pouches Wintergreen, Skoal Pouches Mint, Kodiak Pouches Wintergreen; 4) Grizzly Fine Cut Regular; 8) Copenhagen Fine Cut Original, Copenhagen Long Cut Straight, Grizzly Pouches Straight, Skoal Long Cut Classic, Skoal Long Cut Wintergreen, and Dual Users of Camel and Marlboro Snus and cigarettes.

Exclusion criteria include:

- a) currently using other tobacco (>1 episode of smoking per week on average; no combustible tobacco use in the last 21 days and CO >8 ppm) or nicotine products;
- b) female subjects pregnant or nursing;
- c) use of alcohol within the last 24 hours of testing and no more than 21 drinks per week at phone screening;
- d) use of any inhalable drugs in the last 14 days and regular use >1 times per week;
- e) current infection or use of antibiotics;
- f) active liver or kidney disease, or UTI which would interfere with biomarker measures.

Subjects meeting these criteria will then be asked to come into the research clinic for an orientation visit, to provide informed consent, and to engage in more thorough screening. Subjects will also be required to complete a tobacco use questionnaire, medical history form (which will be reviewed by a physician), and baseline measurements (see below).

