### ***B2d. Tobacco Products***

For Study 1, usual brand of ST products will be used. We chose products that had substantial market share and showed a range in nicotine level and in NNK and NNN levels [4, 46, 75, 151]. Table 2 shows the brands that were chosen for testing. Free/unprotonated nicotine levels were considered high (H) if they were > 5 mg/g, medium (M) if they were between 2-5 mg/g and low if they were < 2 mg/g [3]. TSNA levels were based on a classification that was developed by [name] ([name], report for WHO, TobReg). High (H) levels were NNN plus NNK > than 10 µg/g, Medium (M) levels were NNN plus NNK from 2-10 µg/g, and Low (L) levels were NNN plus NNK < 2 µg/g. Products that are in the Low range for both nicotine and TSNAs tend not be manufactured.

Table 2

Group	Product	Test Date	# Tins/ Regions	Nicotine (mg/g wet)	NNK+NNN (µg/g wet)	Nicotine Group	TSNA Group
1	Camel Snus (All Flavors)	Fall 2010		2.65		Low	Low
	Marlboro Snus (All Flavors)						
	Skoal Long Cut Mint	Fall 2011	3 / 2	1.2	1.23		
	Skoal Fine Cut Original	Spring 2011	1 / 1	2.79	1.88		
2	Copenhagen Long Cut Original	Fall 2010	1 / 1	3.51	2.55	Med	Med
	Kodiak Wintergreen	Spring 2010	9 / 3	4.51	2.73		
	Skoal Bandits Wintergreen	Spring 2010	11 / 3	3.05	3.72		
	Skoal Pouches Straight	Spring 2011	1 / 1	4.02	2.58		
	Skoal Pouches Wintergreen	Spring 2011	1 / 1	3.89	2.81		
	Grizzly Long Cut Straight	Spring 2010	5 / 2	4.23	3.84		
	Skoal Long Cut Straight	Spring 2010	9 / 3	3.15	3.11		
3	Grizzly Long Cut Mint	2010 summary		7.58	3.72	High	Med
	Grizzly Long Cut Wintergreen	Spring 2010	4 / 2	5.12	3.05		
	Grizzly Pouches Wintergreen	Spring 2011	1 / 1	6.25	3.71		
	Skoal Pouches Mint	Spring 2011	1 / 1	5.19	2.15		
	Kodiak Pouches Wintergreen	Spring 2011	1 / 1	5.88	3.44		
4	Grizzly Fine Cut Regular	Spring 2011	1 / 1	4.41	15.3	Med	High
6	Kodiak Long Cut Mint	Spring 2011	1 / 1	3.9	1.91	Med	Low
	Kodiak Long Cut Straight	Spring 2011	1 / 1	4.06	1.88		
8	Copenhagen Fine Cut Original	Spring 2010	9 / 3	2.43	3.45	Low	Med
	Copenhagen Long Cut Straight	2010 summary		2.56	2.07		
	Grizzly Pouches Straight	Spring 2011	1 / 1	0.48	4.0		
	Skoal Long Cut Classic	Spring 2011	1 / 1	2.88	2.88		
	Skoal Long Cut Wintergreen	Spring 2011	1 / 1	2.7	2.51		

Nicotine Group	mg/g wet weight
Low	<3
Medium	3-5
High	>5

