## **C2. Power Considerations:**

The goal is to enroll 100 subjects for each of the six brands listed in Table 2. The mean toxicant uptake level is expected to vary between brands; however, the standard deviation (SD) should

be similar for all brands. This is the common SD and is equivalent to the root of the Mean Square Error (MSE) from the one-way ANOVA. With a total of 600 subjects, this F-test will have 92% power to detect a significant difference at the 0.05 level if the brands with the largest and smallest means differ by at least one-half the common SD. Therefore, if the common SD for the biomarker was 10 units, then there would be a 92% chance that we find a significant difference between brands if the biggest and smallest means were at least 5 units apart. This analysis was done using Power Analysis and Sample Size (PASS) 2005 by NCSS, Inc.

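### Inclusion criterion d leaves out both Group 6 products of Table 2, so one of the six groups the plan relies on cannot be enrolled as written

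*Combined protocol and SAP*

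**What the plan says.** - **Eligibility (B2a, criterion d).** A subject must use one of the listed products. The list is numbered 1, 2, 3, 4, 8, and the run at issue reads "4) Grizzly Fine Cut Regular; 8) Copenhagen Fine Cut Original, Copenhagen Long Cut Straight, Grizzly Pouches Straight". It ends with a category of dual users of snus and cigarettes.
- **Product table (B2d, Table 2).** There are six groups, numbered 1, 2, 3, 4, 6 and 8. Group 6 consists of "Kodiak Long Cut Mint" (3.9 mg/g nicotine, 1.91 µg/g NNK+NNN) and "Kodiak Long Cut Straight" (4.06 mg/g, 1.88 µg/g), labelled medium nicotine and low TSNA.
- **Recruitment (B1 and B2).** B1 states: "Subjects using the brands listed in Table 2 will be recruited from three different regions in the U.S". B2 sets N=600, 200 per site, with 100 for each Table 2 brand.
- **Analysis (C1).** Aim 1 is a one-way ANOVA across six brands, followed by Tukey comparisons. Aim 4 weights six brand means by market share.
- **Product testing (B2c, B2e).** Ten subjects for each of six brands at three sites supply tins, 180 in all.
- **Power (C2).** "The goal is to enroll 100 subjects for each of the six brands listed in Table 2". For N=600 the section claims that "this F-test will have 92% power to detect a significant difference at the 0.05 level". The condition attached to this claim concerns the spread of the group means: "the brands with the largest and smallest means differ by at least one-half the common SD".

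**The concern.** A site that follows criterion d must turn away every Group 6 user, while the rest of the plan counts on 100 of them. Subjects refused at screening cannot be recovered at analysis.

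The stated goal in section A is to compare exposure across brands that differ in nicotine and in TSNAs, and Table 2 is arranged on those two factors. An empty cell therefore removes specific comparisons between product types as well as lowering the headcount.

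**Working it through.** **1. Cross-match of the two lists.** Criterion d: 2 + 7 + 7 + 1 + 5 = 22 products in groups 1, 2, 3, 4 and 8. Table 2: 4 + 7 + 5 + 1 + 2 + 5 = 24 products in groups 1, 2, 3, 4, 6 and 8. Every product in criterion d is in Table 2. The two in Table 2 but not in criterion d are exactly the two Group 6 products, and they appear under no other number. The text runs on without a break from 4) to 8), so this is not a gap from PDF reading.

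**2. What the plan means by a brand.** Six brands at 100 each give 600 only if a brand is a Table 2 group; 24 products at 100 each would be 2,400. Group is used in that sense below.

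**3. Counts.** Subjects: 6 × 100 = 600 planned; 5 × 100 = 500 from the eligible Table 2 groups. Tins: 10 × 6 × 3 = 180 planned; 10 × 5 × 3 = 150.

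**4. Contrasts, by Table 2's labels.**

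| Nicotine | Low TSNA | Medium TSNA | High TSNA |
|---|---|---|---|
| Low | Group 1 | Group 8 | none |
| Medium | Group 6 | Group 2 | Group 4 |
| High | none | Group 3 | none |

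- Pairs at the same nicotine level: four with Group 6 (1–8, 6–2, 6–4, 2–4), two without it (1–8, 2–4).
- Pairs at the same TSNA level: four with Group 6 (1–6, 2–3, 2–8, 3–8), three without it. The lost pair, 1–6, is the only nicotine comparison at low TSNA.
- Medium nicotine is the only row with all three TSNA levels, and it loses its low end. Groups 1, 8, 6 and 2 are the only complete two-by-two block of nicotine by TSNA.

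**5. Power.** Inputs from C2: n = 100 per group, alpha 0.05, range of means 0.5 SD. C2 does not say where the intermediate means lie, so two patterns are shown. In SD units the noncentrality is λ = n × Σ(mean − grand mean)². Power is the upper tail of the noncentral F with k − 1 and N − k degrees of freedom.

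The plan's figure first: six equally spaced means are ±0.25, ±0.15 and ±0.05. The sum of squares is 2 × (0.0625 + 0.0225 + 0.0025) = 0.175, so λ = 17.5 and power is 91.6%. This reproduces the stated 92%.

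Five equally spaced means are ±0.25, ±0.125 and 0. The sum is 2 × (0.0625 + 0.015625) = 0.15625, so λ = 15.6 with 100 per group. With the other means at the midpoint the sum is 2 × 0.0625 = 0.125 for any number of groups.

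| Design | df | Equally spaced: λ, power | Others at midpoint: λ, power |
|---|---|---|---|
| 6 × 100 | 5, 594 | 17.5, 91.6% | 12.5, 78.4% |
| 5 × 100 | 4, 495 | 15.6, 90.2% | 12.5, 81.6% |
| 5 × 120 | 4, 595 | 18.75, 95.0% | 15.0, 88.8% |

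Within a pattern, dropping Group 6 at 100 per group costs 1.4 points or gains 3.2. The gain arises because λ is unchanged while the numerator degrees of freedom fall from 5 to 4.

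**The case against.** The strongest reply is that B1, B2 and C2 all direct recruitment to Table 2, so this is a contradiction between two lists and not a design with a proven empty cell. That stands: the documents do not show which list was intended. It does not remove the problem, because criterion d decides who is enrolled.

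Four stronger readings are tempting, and the documents do not support them.

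- **TSNA can no longer be separated from nicotine.** Group 8 is low nicotine and medium TSNA and is eligible, so Group 1 versus Group 8 compares TSNA levels at low nicotine. In addition, no TSNA contrast within a nicotine level is a named test: Aim 1 is the ANOVA with Tukey comparisons, and Aim 2 uses correlations with constituent levels and regression on patterns of use.
- **Power falls from 92% to 82%.** The 92% needs roughly equally spaced means, and the 82% puts the other means at the midpoint. Like for like there is no material loss.
- **Both lists were fixed in one revision, so the omission is a slip.** The revision history says the 7/13/11 change covered eligibility and page 9. Nothing shows that page 9 is Table 2, and Table 2 carries a Fall 2011 test date.
- **Dual users are the sixth group.** They are not in Table 2, and exclusion a bars anyone smoking more than once a week on average.

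One further reservation stands. The cell argument uses Table 2's labels and its key, where medium nicotine is 3–5 mg/g. The B2d text gives 2–5 mg/g. On that scale the eligible Skoal Fine Cut Original (2.79 mg/g, 1.88 µg/g) would itself be medium nicotine and low TSNA.

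**Conclusion.** The inconsistency is real and affects enrolment. As written, criterion d excludes one of the six groups required by the recruitment target, tin count, primary ANOVA, market-share weighting and power statement. At 100 per group, 500 subjects and 150 tins would come from Table 2 groups in place of 600 and 180.

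The scientific loss is bounded: the low-TSNA cell at medium nicotine, and the only comparison of nicotine levels at low TSNA. Low versus medium TSNA at low nicotine (Group 1 versus 8) and medium versus high TSNA at medium nicotine (Group 2 versus 4) remain. A five-group ANOVA could still be run with nearly the same omnibus power.

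This rests on reading brand as Table 2 group, on Table 2's own labels, and, for the 91.6% and 90.2%, on equally spaced means with a common SD.

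**What to change.** Reconcile B2a criterion d with Table 2 in one of two ways.

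- **Group 6 is intended.** Add Kodiak Long Cut Mint and Kodiak Long Cut Straight to criterion d. The six-group counts and power statement then stand.
- **Group 6 was dropped on purpose.** Remove it from Table 2, change six to five in B2c, B2e, C1 and C2, and restate the tin count (150). Restate N and power with the assumed pattern of means: about 90% for five groups of 100 with equally spaced means, or 95% if 600 is kept at 120 per group. The totals of 600 and 200 per site in B2 need the same check. State that at medium nicotine TSNA is compared only between Groups 2 and 4.

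In the same amendment, reconcile three related points:

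- Four products sit in different groups in the two lists. Skoal Long Cut Mint and Skoal Fine Cut Original are in Group 1 in Table 2 and group 2 in criterion d. Grizzly Long Cut Straight and Skoal Long Cut Straight are in Group 2 in Table 2 and group 3 in criterion d.
- B2d gives two ranges for medium nicotine, 2–5 mg/g in the text and 3–5 mg/g in the key.
- The dual-user category is absent from Table 2 and conflicts with exclusion a. The plan should say whether these subjects count toward N and enter the ANOVA.

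The cost is a short text amendment with no new procedure. It should be made before criterion d is used for further screening.

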### **B2b. Measures and Schedule of Administration**

The following provides the measures that will be administered. Table 1 describes the measures to be obtained and the timing of the measurement. The majority of these measures have been used in our prior studies and have been found to be dose-sensitive to change in amount of smoking or ST use, or sensitive to switching products (e.g., conventional cigarettes to modified cigarettes, cigarettes to ST products).

Table 1. Schedule of visits and measures Study 1

	Visit	
	Orientation	1
Consent	X	
Baseline and Moderator Measures		
Demographics	X	
Medical History and Concomitant meds	X	X
Tobacco Use History and Exposure,	X (brief)	
Severson ST Dependency Scale	X	
Perceived Health Risk	X	X
Stages of Change		X
CES-D		X
PANAS		X
Perceived Stress Scale		X
Michigan Alcohol Screening Test,		X
NIAAA Alcohol Use Questionnaire		
Exposure and Lifestyle Measures		
Occupational Health History		X
ETS and Social Influences		X
Dietary – consumption of meats		X
IPAQ		X
Medical status (e.g., infections)		X

Novel Determinants and Measures of Smokeless Tobacco Use: Study 1

Daily Tobacco Use Diary	X (start at screen)	X
Vitals (Blood pressure and heart rate)		X
Weight		X
Concomitant Medications		X
Carcinogen Exposure Urinary total NNAL Total NNN Nitrosoamino acids NPRO and MNPA Phenanthrene tetraol 1-hydroxypyrene (1HOP)		X
Cardiovascular Measures (UMN only) Lipoproteins C-reactive protein Fibrinogen WBC		X X X X
 Buccal assay		X
 Nicotine and metabolites	X	X
 Product Constituent Testing		X
 Weight per dip	X	X
Carbon Monoxide		X

Buccal assays to be placed in biorepository for future analyses (UMN only)

Urinary total nicotine equivalents and nicotine metabolite ratio (3-HC:cotinine)

Product constituent testing will be conducted on a random sample of 30 tins for each brand of ST (10 brands from each site)

Estimated weight per dip will be calculated by averaging the weight of 3 typical daps

### **B2bi. Subjective Measures**

1) Demographics such as age and gender, socioeconomic status and if possible, self-reported race or ethnicity.

2) Tobacco Dependence as assessed by the Severson Smokeless Tobacco Dependency Scale (SSTDs). This scale consists of 8 items and a total score is calculated as the sum of items 2 through 8. The Cronbach coefficient alpha for the SSTDs was 0.69. Candidate items for this scale were drawn from the following sources: a version of the Fagerström scale used in previous studies [101, 102]; a version of the Cigarette Dependence Scale (CDS) with 5 items (CDS-5) [103] adapted for smokeless tobacco users.

3) Tobacco Use History and Exposure Questionnaire is an interview with variables such as age of initiation of ST use, amount of use, brand used, duration of use, number of quit attempts, duration of quit attempts, and current and past other tobacco product use. Tobacco use questions are taken from a national survey (Tobacco Use Supplement to the Current Population Survey) so that comparisons can be made with national samples.

4) Centers for Epidemiological Studies-Depression (CES-D) is a 20-item scale which assesses current symptoms of depression that has been used in the general population [105].

5) Michigan Alcohol Screening Test (MAST) Short form assesses any negative consequences from alcohol use by self report [106] and the NIAAA Alcohol Use Questionnaire examines rate of alcohol use, in the last 3 months

6) Positive Affect Negative Affect Scale (PANAS-X) [108] has been used in studies to assess negative affect prior to and after cessation [e.g., 109]. This scale contains two higher order scales, positive and negative, and 11 specific affects. We will be focusing primarily on the negative affect scale, which measures subjective distress and unpleasant engagements (aversive mood states such as anger, disgust, guilt, fear and nervousness).

7) Perceived Stress Scale is a 14-item scale that measures self-perceived stressful situations in the last month. The items reflect the extent to which the respondents find that their lives are unpredictable, uncontrollable and overloading [110]. Each item is rated on a 0 to 4 scale that ranges from 0=never and 4=very often. The Cronbach's alpha observed in one study was 0.80 (Manning et al., 2005). The scale has been related to smoking status and cessation [e.g., 111, 112, 113].

8) Perceived Health Risk form assesses perceived health risk of the product for different disease states (heart disease, oral cancer, lung cancer, diabetes, etc.). Subjects rate the product on a 0 to 10 rating scale (0=no risk to 10=very high risk). We have used this scale in a number of tobacco evaluation studies [e.g., 98].

9) Stages of Change assessing intention of quitting in the next 30 days and 6 months.

10) Environmental and Social Influences on Tobacco Use consists of a questions regarding: a) tobacco use (ST, cigarettes and other nicotine containing products) among the subject's social network (e.g., significant other, friends, co-workers, siblings and parents); b) extent of social support for or against ST use; c) restrictions or bans on smokeless tobacco (and smoking) at work, school or in the home; and d) cost of smokeless tobacco products (unit price) and income. These are variables found in studies to be associated with uptake and amount of tobacco use.

11) Food frequency questionnaire for cooking practices assesses frequency of eating charred and processed meats within the last week.

12) Modified International Physical Activity Questionnaire (IPAQ) interview assesses physical activity by recall 7 question assessment of moderate, hard and very hard physical activity engaged in week days and week ends modified to cover the last three months average activity.

<http://www.ipaq.ki.se/>.

13) Medical History and Concomitant Medications lists current diagnosis, symptoms, medications and past health problems, and a record of use of any over-the-counter and prescription medications.

14) Environmental and Occupational Health History assesses environmental and occupational toxicant exposures, which might affect our biomarker measures [124].

15) Tobacco Use Status will be assessed using a *Tobacco Use Questionnaire* that asks about current tobacco use status (ST and other tobacco products). This questionnaire will be administered at the clinic visit. The daily diary cards will collect similar information, but will be hand recorded and returned during the clinic visit. The daily diary cards will be used in Study 1 to conserve costs. We have successfully used daily diary cards in the past when examining the relationship between exposure measures and ST topography [41, 42, 44, 76].

